## **Materials and Method**

### **Inclusion criteria**

- 20 study participants with T2DM (definition (49)) will be recruited:
- Group 1: 10 men/women with NAFL and/or NASH, confirmed fat fraction (FF) % > 5,6 assessed using MR spectroscopy (MRS)
- Group 2: 10 men/women matched for age and BMI without NAFLD (definition (47))
- Age of 30-70 years
- Non-smokers
- Written consent before the study start

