## Flow chart

## Screening

The purpose of the visit is to evaluate inclusion and exclusion criteria. Prior to the visit, the potential candidate participant has already received written information material about the project. The potential candidate will be informed orally. If the participant accepts final participation and is eligible to participate in the study, a declaration of consent is signed. Furthermore, during this visit following will be obtained:

**- Medical history and examination (incl. Weight, height, blood pressure and pulse), blood tests (plasma glucose, hemoglobinA1C, lipid profile, SD163, haematological parameters, TSH, ALAT, ASAT, alkaline phosphatase, eGFR, creatinine, sodium and potassium).**

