### **Statistical analysis**

Sample sizes are based on estimates of cardiac palmitate from two recent studies in type 2 and nondiabetic men (28,29), as well as on prior experience regarding mean basal VLDL-TG secretion of 60  $\mu\text{mol}/\text{min}$  (SD of diff: 10  $\mu\text{mol}/\text{min}$ ). To detect a difference in palmitate oxidation as well as on VLDL-TG secretion between 2 experimental days of 20% (12.5 (SD 6.25)  $\mu\text{mol}/\text{min}$ ) with power 0.80 and  $\alpha$  5%, seven subjects are needed using two-sample t-test. Group comparisons will be done with standard statistical methods (ANOVA, t-test for parametrical data) and p-value under 0,05 will be assumed to be statistical significant. Corrections will be examined using Pearson's or Spearman's test. With 10 participants in each group, we would be able to determine a 30 % increased uptake of FFA in liver in subjects with NAFLD (power: 0.80). This is based on estimates of palmitate uptake in liver and FA oxidation in the heart from our previous studies, where we used the same  $^{11}\text{C}$ -palmitate tracer (37,50).

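### The groups are matched on age and BMI, but the named group comparison uses neither variable, so precision may be forgone and residual imbalance goes uncorrected

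*Combined protocol and SAP*

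**What the plan says.** The Inclusion criteria set the size and the design: "20 study participants with T2DM (definition (49)) will be recruited", with "Group 2: 10 men/women matched for age and BMI without NAFLD" as the comparison group. They do not say whether matching is person to person or by group, and they give no tolerance.

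The Statistical analysis section is the only analysis text. For the group comparisons it states "Group comparisons will be done with standard statistical methods (ANOVA, t-test for parametrical data", and that a "p-value under 0,05 will be assumed to be statistical significant". Its sizing sentence ends "seven subjects are needed using two-sample t-test". Age, BMI, pairs and matched sets do not appear there.

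The matching variables will be on file. Age is an eligibility criterion, and the Screening visit records "Medical history and examination (incl. Weight, height, blood pressure and pulse", from which BMI follows.

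**The concern.** Matching makes the two groups alike on age and BMI. Whatever those variables contribute to an outcome then largely cancels from the difference between the group means. An unadjusted t-test or one-way ANOVA does not know this: it leaves the age and BMI variation in its error term. If that variation is real, the reported standard error exceeds the true one, the interval is wider than it need be and the actual type I error is below 5%.

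There is a second consequence. This is an observational comparison of people with and without NAFLD. Where matching is imperfect, an age or BMI difference between the groups can remain, and an unadjusted test does nothing about it. With 20 people and a planned power of only 0.80, both matter.

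**Working it through.** **Inputs from the documents.** 10 per group; alpha 5% (taken as two-sided); power 0.80; sizing difference 12.5 with SD 6.25; a 30% increase in liver FFA uptake stated as detectable with 10 per group.

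**Inputs assumed.** R², the share of within-group outcome variance explained by age and BMI together, and the closeness of matching. The documents give neither, so both are varied.

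**1. The plan's own figure.** d = 12.5/6.25 = 2.0. A two-sided two-sample t-test (noncentral t) needs 6 per group for power 0.80, and 7 per group gives 0.93. The stated seven is reproduced to within one, by an unpaired test without covariates.

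**2. Effect used for the comparison.** With 10 per group, an unadjusted t-test has power 0.80 at d = 1.325. For the 30% statement this implies a coefficient of variation of 30/1.325 = 22.6%.

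**3. Standard error under exact balance.** The unadjusted test estimates σ√(2/n). The true value is σ√(1−R²)·√(2/n). The ratio is 1/√(1−R²):

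- R² = 0.1: 1.05
- R² = 0.2: 1.12
- R² = 0.4: 1.29

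Simulated with pairs matched to about 0.2 SD, the excess is about 9% at R² = 0.2 and 27% at 0.4.

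**4. Power of the adjusted model under exact balance.** Noncentrality = d√(n/2)/√(1−R²) = 1.325 × 2.236/√(1−R²), on 16 degrees of freedom (critical t 2.12, against 2.10 on 18):

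- R² = 0: 2.963, power 0.794
- R² = 0.02: 2.993, power 0.802
- R² = 0.1: 3.123, power 0.834
- R² = 0.2: 3.312, power 0.875
- R² = 0.4: 3.825, power 0.948

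**5. Both tests under two degrees of matching, by simulation.** *Tight*: pairs within about 0.2 SD on both variables. *Loose*: the best 10 pairs from 15 people with and 15 without NAFLD. The section on the scope of screening expects 30 screened to obtain 20; the 15/15 split, standard-normal covariates with the same distribution in both groups, and no screening failures are assumptions. Runs used 6,000 to 20,000 trials per setting, so the Monte Carlo standard error of a power near 0.80 is about 0.003 to 0.005.

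| R² | t-test type I error, tight / loose | Power at d = 1.325, t-test v adjusted: tight | Same: loose |
|---|---|---|---|
| 0 | 0.05 / 0.05 | 0.80 v 0.79 | 0.80 v 0.77 |
| 0.1 | 0.040 / 0.047 | 0.81 v 0.83 | 0.82 v 0.83 |
| 0.2 | 0.03 / 0.041-0.046 | 0.83 v 0.88 | 0.83 v 0.86 |

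At R² = 0.4 the t-test's type I error is 0.016 (tight) or 0.030 (loose), and power is about 0.85 v 0.94.

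**6. Matching by group only.** With no pairs, and covariate means aligned to about 0.1 SD, the t-test's type I error is 0.039, 0.031 and 0.015 at R² = 0.1, 0.2 and 0.4. Power is 0.81 v 0.83, 0.82 v 0.87 and 0.85 v 0.95. The result does not need pairs to exist.

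**7. Break-even.** Adjustment starts to pay at about R² = 0.02 under close balance and about R² = 0.10 under loose matching.

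**The case against.** The strongest reply is that nothing in the plan is invalid. At worst the t-test is conservative, and in the scenarios above its power at the detectable effect stays at about 0.80 or rises. The main purpose of matching here, making the groups comparable on age and BMI, survives an unadjusted test. All of this stands, and it makes the point one of efficiency.

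It is also fair that the wording is open. The group-comparison sentence does not rule out a covariate or a paired test; the words on two samples belong to the sizing sentence, which speaks of a difference between two experimental days. This stands in part. The only test specified is unpaired, and if the wording is open then the plan still does not say how the matching enters the analysis.

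Three stronger readings are tempting, and the documents do not support them:

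- *Every reported interval is too wide.* That holds only for outcomes that age or BMI predicts. The documents give no such figure for the cardiac primary endpoint or for any secondary one.
- *The benefit of matching is lost.* Comparability is kept. What is forgone is a possible further gain in precision.
- *The data are pairs and need a paired t-test.* Individual pairing is not stated. With 9 degrees of freedom, a paired test beats the unpaired one only above a within-pair correlation of about 0.15, and at zero correlation its power is 0.751 against 0.800.

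Finally, tight matching cannot be presumed. With about 30 people screened and group known only after the MRS scan, matches may be loose. The conservatism then shrinks, and the cost of adjusting for useless covariates rises from about 1 point to about 3. This also stands. But loose matching is also where leftover imbalance is most likely, and only the adjusted model corrects it.

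**Conclusion.** The concern holds conditionally. The design uses age and BMI and the named analysis does not. If these variables explain a fair share of outcome variance, the unadjusted analysis gives up roughly 3 to 5 power points at R² = 0.2 and about 9 at R² = 0.4, always at d = 1.325. If they explain nothing, adjustment loses about 1 to 3 points. These sizes rest on assumed values of R² and of matching closeness, and on a two-sided test. The omission and its mechanism are clear from the text; the magnitude cannot be settled from it. The separate gain, correction of any imbalance that matching leaves, is not quantified, because the documents give no basis for its size or direction. The label is cheap improvement.

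**What to change.** In the Statistical analysis section, make the group comparison a linear model with group, age and BMI as terms. Report the adjusted difference with its 95% CI, and keep the unadjusted t-test as a supportive analysis. Say in the same place whether matching is individual or by group. Fixing this before the data are seen also prevents a later choice between adjusted and unadjusted results.

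The cost is a sentence or two and two residual degrees of freedom (18 to 16), with the small power loss given above if age and BMI turn out to be unrelated to the outcome. No new data are needed.

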### **The scope of the screening activity**

We expects to screen 30 potential candidate participants, who full fill inclusion criteria with scans and blood samples to obtain 20 participants. The test results from the blood samples from screening of volunteers who are being included or excluded, will be available in the volunteers electronic patient journal (MidtEPJ). If the blood samples or scans gives rise to further investigation, the participant will be contacted by phone and informed to contact a medical doctor/or be referred to the relevant medical speciality.

### **Analysis and interpretation**

Data will be kept in an anonymised form and archived in the Department of Endocrinology and Internal Medicine (DOH), AUH. Data will be handled according to guidelines appointed by the Danish Data Protection Agency. The results are expected to be published in articles in peer-reviewed international scientific papers.

### **Feasibility of the study**

The Medical Research Lab has significant expertise in conducting clinical and metabolic studies and all the methods are well established in the lab.

### **Economy and insurance**

None of the participating researchers has an economical interest in this project. The salary for Ph.D. student [name] is finance by Danish Diabetes Academy (DDA) and Steno Diabetes Center Aarhus, SDCA, Aarhus University Hospital. Project costs will be covered by a grant from the Novo Nordisk Foundation. Participants will receive remuneration for their participation (2500 DKK in total taxable amount) and have their transportation cost paid. The study patients will be covered by a mandatory insurance in the Danish Healthcare system ("Lov om klage- og erstatningsadgang indenfor sundhedsvæsenet").

### **Ethical aspects**

All studies will be conducted in accordance with the articles of the Declaration of Helsinki. The protocol will be approved by the Health Research Ethics Committee of Central Region, Denmark, the Danish Data Protection Agency. Care will be taken to administer the lowest tracer dose possible. In addition as mentioned above, the study participants will be covered by a mandatory insurance in the Danish Healthcare system ("Lov om klage- og erstatningsadgang indenfor sundhedsvæsenet").

### **Informed consent**

By request "Project information" and "Information material from The Denmark Central Region Committees on Health Research Ethics" will be sent to the potential candidate participant by post or by email. A meeting with the investigator is then arranged in order to give oral information about the project and to evaluate inclusion and exclusion criteria. The meeting will take place at the Department of Internal Medicine and Endocrinology, AUH, and if the participant wishes to, the participant can bring an assessor.

All information about the study will be given by investigator [name]. This project is a scientific trial and it will be stated clearly in both oral and written information material. Likewise, aims, risks and annoyances and potential benefit of this study will be stated. It will be emphasized that participation is on a voluntary basis and that consent can be withdrawn at any time without consequences for the participant.

If the participant accepts to participate, a declaration of consent is signed.

### **Safety evaluation**

## **Advantages**

We consider participation in this study to be safe and tolerable. Advantages and any potential side effects and annoyances will be described in the following.

As part of the study, participants will have measured their lipid profile, blood sugar, insulin resistance, body composition, haematological parameters, liver, and kidney function. If any of these parameters suggests an increased risk of developing liver, cardiovascular, or diabetic complications the participants will be offered counselling and guidance at the end of the study.

In addition, many patients with diabetes will see it as meaningful to contribute with new knowledge about perturbations in fatty acid metabolism that on a short term may have implications in the treatment of NAFL and NASH.

## **Side effects and annoyances**

Participants may experience discomfort in connection with placement of a venous catheter and there is a risk of developing a bruise. Placement of arterial cannula is associated with some discomfort and there is a minimal risk of developing arterial thrombosis, however, this procedure is only used in the rare cases where the venous catheter is not usable and is performed by trained personnel. Muscle and fat biopsies is associated with some discomfort / pain as well as a small risk of developing blood clots and infection at the injection site. The participants will be asked to contact the study responsible medical doctor [name] or the Emergency Department, AUH, for signs of infection (redness, heat, soreness, swelling) or major blood clot.

The total blood loss in connection with blood sampling and biopsies will amount to approx. 400 ml (over all study days) and will therefore not be a problem in healthy non-anaemic individuals.

The long-term risk of participation in the study is only related to the radiation exposure. The total radiation load is 5.03 mSv, corresponding to 1.7 times the radiation you normally receive in Denmark during a year (background radiation approx. 3 mSv per year) (63). Theoretical calculation of the extra risk of participating in the trial will be approximately 0.03% increased risk of contracting a cancer during one's lifetime, and an average Dane will thus increase his risk from approx. 25.00% to 25.03%.

## **Biological material, biobank and handling of data**

The following samples will be obtained from each participants:

- 2 x 2 fat biopsies, one from subcutaneous adipose tissue on the abdomen and one from femoral adipose. 2 x 1 muscle biopsy from m. vastus lateralis. All procedures are performed under sterile conditions and with local anesthesia as well as subsequent cooling of the area with ice and compression to ensure rapid hemostasis. An average amount of 200 mg pr. sample is collected. A research biobank is set up, where the samples are frozen with liquid nitrogen for later analysis.
- Blood samples of 400 ml in total are collected. A research biobank is set up, where the samples are frozen with liquid nitrogen for later analysis. From trial participants who only participate in the screening trial, approx. 30 ml of blood.

If there is biological material left at the end of the experiment, the material will be transferred to the research biobank for future use. The data protection rules continue to apply so that the Health Research Ethics Committee must approve new research in the biological material and new informed consent must be obtained. Excess material will be stored for 15 years after the end of the project. The excess biological material from subjects excluded after the screening visit will not be transferred to a biobank for future research.

### **Biobank for future research**

Blood- and tissuesamples are expected to be used in the analysis. If there are biological material left in the ending of the investigation (blood and muscle- and adipose tissue) left, the leftover material will be transferred to the research biobank for future use and will be kept for 15 years after the ending of the investigation. We would like to keep the material in a biobank, as we in a few years to come, would investigate if NAFL and NASH is affected by other systems, that we currently do not have the knowledge of. The data protection rules continue to apply, so that the Ethics Committee must approve new research in the biological material and new informed consent must be obtained. The excess biological material from subjects excluded after the screening visit will not be transferred to a biobank for future research.

### **Handling of data**

After informed consent, information about the medical history, comorbidity, blood sample tests, test results from scans and other information relevant for the study will be registered and will be extracted from the patient journal. Project investigator will have direct access to patient files (MidtEPJ).

Data will be kept in an anonymised version on AU's server in REDCap for 15 years after the termination of the investigation and temporarily in Department of Endocrinology and Internal Medicine, AUH. REDCap will be used as electronic CRF (case report form).

Data will be handled according to guidelines appointed by the Danish Data Protection Agency.

